6.0 DOSE MODIFICATIONS FOR ADVERSE EVENTS

The Study Chair must be notified of any dosage modification or use of myeloid growth factor.

6.1 Dose Modifications for Hematological Toxicity

- 6.1.1 Patients who have dose-limiting thrombocytopenia or neutropenia (defined in [section 5.2](#), [section 5.2.1](#) and [section 5.5.2](#)) should receive subsequent cycles with at least a 25% dose reduction (75% of the original dose). Please see dosing nomograms in [Appendix V](#). For patients ≥ 18 years of age with starting dose of 40 mg BID, dose should be reduced to 30 mg BID 3 days on, 4 days off per week (25% dose reduction).
- 6.1.2 Patients who experience dose-limiting thrombocytopenia and/or neutropenia (as defined [in Section 5.5.2](#)) after one dose reductions must be removed from protocol therapy.
- 6.1.3 Patients who have a dose-limiting hematological toxicity that does not resolve to eligibility parameters within 14 days after the planned start of the next treatment cycle (42 days from start of previous cycle) must be removed from protocol therapy.

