5.2 Criteria for Starting Subsequent Cycles

A cycle may be repeated every 28 days if the patient 1) has at least stable disease 2) all pre-cycle studies required per [Section 8.1](#) meet eligibility criteria-as defined in [Section 4.0](#) and 3) is otherwise eligible to continue agent administration per the requirements in [Section 6.0](#).

5.2.1 Recommendations for Starting Each Weekly 3-day Course:

BAY 1895344 (elimusertib) is administered on a 3-day on and 4-day off schedule, repeated 4 times each cycle. Hematologic toxicities are the most common toxicities with BAY 1895344 (elimusertib). Eligibility criteria require an ANC \geq 1000/ μ L and Platelets \geq 100,000/ μ L, hence these parameters also need to be met to start any cycle (See [section 4.1.11.1](#)). Once a cycle has started, patients are required to have an ANC $>$ 500/ μ L and Platelets $>$ 50,000/ μ L within 48 hours prior to initiation of each 3 day interval of BAY 1895344 (elimusertib) administration (i.e. ANC and platelet parameters must be met (without transfusion) within 48 hours of initiation of days 8, 15, and 21). If parameters are not met, this 3-day interval of BAY 1895344 (elimusertib) will be omitted and attempted to restart the following week (e.g. day 15 or 21). If more than one 3-day block of BAY 1895344 (elimusertib) is missed within a cycle (i.e. $<$ 75% of planned therapy is given for a particular cycle), that would be considered a hematologic DLT.

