5.5 Definition of Dose-Limiting Toxicity (DLT)

DLT will be defined as any of the following events that are possibly, probably or definitely attributable to protocol therapy. The DLT observation period for the purposes of study dose-escalation (Part A) will be the first cycle of therapy. Please refer to [Section 13.5.4](#) for AE resolution definitions

Dose limiting hematological and non-hematological toxicities are defined differently.

5.5.1 Non-Hematological Dose-Limiting Toxicity:**5.5.1.1 Any Grade 3 or greater non-hematological toxicity attributable to protocol therapy with the specific exclusion of:**

- Grade 3 nausea and vomiting of < 3 days duration
- Grade 3 liver enzyme elevation, including ALT/AST/GGT that returns to Grade \leq 1 within 7 days. See [Appendix IV](#) for Adverse Event grading for liver function grading parameters in children and adolescents.

Note: For the purposes of this study the ULN for ALT is defined as 45 U/L.

- Grade 3 hypophosphatemia, hypokalemia, hypocalcemia or hypomagnesemia responsive to supplementation
- Any Grade 2 non-hematological toxicity that persists for \geq 7 days and is considered sufficiently medically significant or sufficiently intolerable by patients that it requires treatment interruption.
- Note: Allergic reactions that necessitate discontinuation of study drug will not be considered a dose-limiting toxicity.

5.5.2 Hematological dose limiting toxicity:

- Grade 4 neutropenia (ANC $< 500/\mu\text{L}$) that persists for \geq 7 days despite holding BAY 1895344 (elimusertib) for 3 days
- Grade 4 thrombocytopenia (Platelet count $< 25,000/\mu\text{L}$)
- Grade 3 thrombocytopenia (Platelet count $< 50,000/\mu\text{L}$) that persists for \geq 7 days despite holding BAY 1895344 (elimusertib) for 3 days *OR* is associated with clinically significant bleeding
- Failure to meet hematological criteria to initiate weekly dosing ([Section 5.2.1](#)) or subsequent cycles of therapy ([Section 5.2](#)) by cycle day 42 (within 14 days of planned start of the subsequent cycle) will be considered dose limiting toxicity.
- Failure to receive at least 75% of the planned number of BAY 1895344 (elimusertib) doses during any cycle (i.e., 9 of 12 planned doses) due to delays attributable to myelosuppression would be considered a hematologic DLT.

5.5.2.1 Note: Grade 3 or 4 febrile neutropenia will not be considered a dose-limiting toxicity.

5.6: THERAPY DELIVERY MAPS (TDMS) FOR CYCLE 1

Page 1 of 1

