Therapy Delivery Map – Cycle 1

This Therapy Delivery Map (TDM) relates to Cycle 1. Cycle 1 lasts 28 days. Please record the dose level in the chart below. Treatment may continue in the absence of unacceptable toxicity. Use a copy of this page once for Cycle 1.

This form is to be completed and uploaded into RAVE at the end of every cycle.

Criteria to start this cycle are listed in [Section 5.2](#). Extensive details are in [Section 5.0](#) and [Section 9.0](#).

This TDM is on 2 pages.

DRUG	ROUTE	DOSAGE	DAYS	IMPORTANT NOTES
BAY 1895344 (elimusertib) IND# [REDACTED]	Oral (Tablet)	_____ mg/m ² /dose BID Dose level 1 max dose = 40 mg BID Dose level -1 max dose = 30 mg BID Part B patients \geq 18 years old: 40 mg BID	1-3 8-10 15-17 22-24	On days that BAY 1895344 (elimusertib) is due to be given, it should be administered twice daily preferably at the same time of day each day. Take BAY 1895344 (elimusertib) one (1) hour before or two (2) hours after a meal with plenty of water.

Assigned Dose Level Ht cm Wt kg BSA m² Age \geq 18 years yes. no

Date Due	Date Given	Day	BAY 1895344 (elimusertib) Nomogram Dose mg qAM. _____ mg qPM	Studies
Enter actual dose administered below				
		PRE	_____ mg _____ mg	a-e, f*, g-i, j^, k, m#, n%, q\$, r@
		1	_____ mg _____ mg	a, b, d, e, f*, g, h, l, o&, p!
		2	_____ mg _____ mg	
		3	_____ mg _____ mg	o&
		4		
		5		
		6		
		7		
		8	_____ mg _____ mg	e, f* 1
		9	_____ mg _____ mg	
		10	_____ mg _____ mg	o&, p!
		11		
		12		
		13		
		14		
		15	_____ mg _____ mg	e, f*, 1
		16	_____ mg _____ mg	
		17	_____ mg _____ mg	
		18		
		19		
		20		
		21		
		22	_____ mg _____ mg	e, f*, j^, 1
		23	_____ mg _____ mg	
		24	_____ mg _____ mg	
		25		
		26		
		27		
		28		

* Please refer to [Section 8.1](#) for the specific timing of these observations.

Observations in Cycle 1

- a. History
- b. Physical Exam
- c. Performance Status
- d. Height, Weight, BSA
- e. Vital Signs
- f. CBC, differential, platelets: *Once weekly. If patients develop Grade 4 neutropenia or Grade 3 or 4 thrombocytopenia, CBC/differential/platelets should be checked at least twice per week (every 3-4 days) until recovery to Grade 3 neutropenia or Grade 2 thrombocytopenia, or until the criteria for dose limiting toxicity are met. For patients who experience hematological dose limiting toxicity, CBCs should be checked at least weekly until recovery of ANC and platelet count to eligibility criteria
- g. SGPT (ALT), Albumin, Bilirubin

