This form is to be completed and uploaded into RAVE at the end of every cycle.

Criteria to start this cycle are listed in [Section 5.2](#). Extensive details are in [Section 5.0](#) and [Section 9.0](#).

This TDM is on 2 pages.

DRUG	ROUTE	DOSAGE	DAYS	IMPORTANT NOTES
BAY 1895344 (elimusertib) IND# [REDACTED]	Oral (Tablet)	mg/m ² /dose BID Dose level 1 max dose = 40 mg BID Dose level -1 max dose = 30 mg BID Part B patients ≥ 18 years old: 40 mg BID	1-3 8-10 15-17 22-24	On days that BAY 1895344 (elimusertib) is due to be given, it should be administered twice daily, preferably at the same time of day each day. Take BAY 1895344 (elimusertib) one (1) hour before or two (2) hours after a meal with plenty of water.

Assigned Dose Level Ht cm Wt kg BSA m² Age ≥ 18 years yes no

Date Due	Date Given	Day	BAY 1895344 (elimusertib) Nomogram Dose mg qAM. mg qPM	Studies
Enter actual dose administered below				
		1	mg mg	a-d, e*, f, g, i, j&
		2	mg mg	
		3	mg mg	
		4		
		5		
		6		
		7		
		8	mg mg	
		9	mg mg	
		10	mg mg	
		11		
		12		
		13		
		14		
		15	mg mg	e*
		16	mg mg	
		17	mg mg	
		18		
		19		
		20		
		21		
		22	mg mg	
		23	mg mg	
		24	mg mg	a-d, h^, j&, k!, l#
		25		
		26		
		27		
		28		

* Please refer to [Section 8.1](#) for the specific timing of these observations.

Cycle 2 +

Required Observations in Cycle 2 +

Page 2 or 2

- a. History
- b. Physical Exam
- c. Height, Weight, BSA
- d. Vital Signs
- e. CBC, differential, platelets: * **Must be obtained within 72 hours of the start of each cycle and on day 15 of all subsequent cycles.** If patients develops Grade 4 neutropenia or Grade 3 or 4 thrombocytopenia, CBC/differential/platelets should be checked at least twice weekly (every 3-4 days) until recovery to Grade 3 neutropenia, Grade 2 thrombocytopenia or until the criteria for dose limiting toxicity are met. For patients who experience hematological dose limiting toxicity, CBCs should be checked at least weekly until recovery of ANC and platelet count to eligibility criteria. Patients who have dose adjustment due to hematologic toxicity attributable to BAY 1895344 (elimusertib), are required to have CBCs once weekly to confirm the safety of this adjusted dose during the cycle. Please see [Section 6.1](#) for details.
- f. SGPT (ALT), Albumin, Bilirubin
- g. Electrolytes including serum creatinine, calcium (Ca⁺⁺), phosphorus (PO₄), magnesium (Mg⁺⁺)

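### After a hematologic DLT met mid-cycle, the plan read literally lets the remaining 3-day blocks of that cycle be given at the unreduced dose

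*Combined protocol and SAP*

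**What the plan says.** Section 6.1.1 covers dose-limiting thrombocytopenia or neutropenia as defined in Sections 5.2, 5.2.1 and 5.5.2. These patients "should receive subsequent cycles with at least a 25% dose reduction (75% of the original dose").

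Section 5.2.1 sets the check before each later block of a cycle: ANC above 500/µL and platelets above 50,000/µL, without transfusion, within 48 hours. A block that fails "will be omitted and attempted to restart the following week". No dose is given for the restart and DLTs are not excepted. The section then adds a DLT of its own: "If more than one 3-day block of BAY 1895344 (elimusertib) is missed within a cycle", the event counts as hematologic dose-limiting toxicity. To open a new cycle, Sections 5.2 and 5.2.1 require the eligibility counts of Section 4.1.11.1: ANC at least 1000/µL and platelets at least 100,000/µL.

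Section 5.5.2 lists the hematologic DLTs. One is "Grade 4 thrombocytopenia (Platelet count" below 25,000/µL), with no duration condition. Others are Grade 3 thrombocytopenia that either lasts at least 7 days despite a 3-day hold or comes with clinically significant bleeding, Grade 4 neutropenia that lasts at least 7 days despite a 3-day hold, and "Failure to receive at least 75% of the planned number of BAY 1895344 (elimusertib) doses during any cycle" because of myelosuppression.

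For non-hematologic DLTs, Section 6.2.1 applies the same minimum 25% reduction to the doses that follow, once laboratory values meet eligibility or the toxicity is Grade 1 or less.

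**The concern.** The two toxicity rules start the reduction at different times. After a non-hematologic DLT the next dose is already reduced. After a hematologic DLT the reduction waits for the next cycle, while the block-restart rule keeps running in the current one. A patient with a declared hematologic DLT could therefore be given the dose that caused it again, with counts only just above 500/µL and 50,000/µL.

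The order is also inverted. The full dose can be repeated in the DLT cycle at counts that would be too low to start the reduced dose in the next cycle.

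Myelosuppression is the drug's main toxicity (Section 5.2.1), and the adult DLTs at the higher doses were predominantly myelosuppression (Section 2.3.2). The rules apply in every cycle and in Part B, where Section 5.3.2 refers sites to Section 6.0 for toxicity. Three sites facing the same event could reasonably continue, reduce or hold.

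**Working it through.** **Can a hematologic DLT be met with blocks still to give?** Blocks start on days 1, 8, 15 and 22 (Section 5.1; Section 5.2.1 prints day 21 for the last check, and day 22 is used here). A block is 3 days × 2 = 6 administrations, so a cycle has 24 administrations over 12 dosing days. The plan's own threshold of 9 of 12 is 75%. One omitted block leaves 3/4 = 75% (no DLT on this criterion) and two leave 2/4 = 50% (DLT).

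- Platelets below 25,000/µL at the day-8 count: block 2 is omitted, blocks 3 and 4 remain.
- The same at the day-15 count: block 3 is omitted, block 4 remains.
- Blocks 2 and 3 both omitted: the DLT is met on day 15 and block 4 remains. Grade 4 neutropenia or Grade 3 thrombocytopenia running from day 8 to day 15 gives the same pattern.
- Either of those lasting, for example, from day 11 to day 18: block 3 is omitted and block 4 remains, as in the day-15 case.
- Grade 3 thrombocytopenia with bleeding needs no duration and can fall at any of these points.
- A DLT found at day 22 leaves no block.

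**Size of the reduction.** Inputs are the starting and reduced doses in Appendix V, as daily totals s and r in mg.

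| Level, BSA (m²) | s | r | 1 − r/s | Appendix V prints | s/r daily | AM ratio, PM ratio |
|---|---|---|---|---|---|---|
| 1, 0.74–0.94 | 40 | 30 | 25.0% | 25% | 1.33 | 1.0, 2.0 |
| 1, 0.95–1.15 | 50 | 30 | 40.0% | 40% | 1.67 | 1.5, 2.0 |
| 1, 1.16–1.35 | 60 | 40 | 33.3% | 35% | 1.50 | 1.5, 1.5 |
| 1, 1.36–1.56 | 70 | 50 | 28.6% | 30% | 1.40 | 1.33, 1.5 |
| 1, ≥ 1.57 | 80 | 60 | 25.0% | 25% | 1.33 | 1.33, 1.33 |
| −1, 0.74–0.94 | 30 | 20 | 33.3% | 35% | 1.50 | 2.0, 1.0 |
| −1, 0.95–1.35 | 40 | 30 | 25.0% | 25% | 1.33 | 1.0, 2.0 |
| −1, 1.36–1.56 | 50 | 30 | 40.0% | 40% | 1.67 | 1.5, 2.0 |
| −1, ≥ 1.57 | 60 | 40 | 33.3% | 35% | 1.50 | 1.5, 1.5 |

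The printed percentages are reproduced, to the nearest 5%, as reductions in daily dose. The unreduced daily dose is 1.33 to 1.67 times the reduced one. Per administration the range is 1.0 to 2.0, because several bands have unequal morning and evening doses.

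**Cycle totals.** The plan is 12s. At 40 mg BID, s = 80 and r = 60, so the plan is 960 mg.

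| Case | Remaining blocks unreduced | Reduced from next dose | Held to next cycle |
|---|---|---|---|
| Day-8 DLT | 9s = 720 (75%) | 3s + 6r = 600 (62.5%) | 3s = 240 (25%) |
| Day-15 DLT | 9s = 720 (75%) | 6s + 3r = 660 (68.75%) | 6s = 480 (50%) |
| Two omitted blocks | 6s = 480 (50%) | 3s + 3r = 420 (43.75%) | 3s = 240 (25%) |

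Across Appendix V, r/s runs from 0.60 to 0.75. Reduction from the next dose therefore gives 55% to 62.5% of plan (day 8), 65% to 68.75% (day 15) and 40% to 43.75% (two blocks).

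**Does another section close the gap?** Section 6.1.3 measures recovery against eligibility counts, but as a removal deadline 14 days after the next cycle's planned start. Section 5.6, observation f, says that after a hematologic DLT "CBCs should be checked at least weekly until recovery of ANC and platelet count to eligibility criteria"; that is monitoring and holds no block. Section 5.7, observation e, says that patients with an adjusted dose "are required to have CBCs once weekly to confirm the safety of this adjusted dose during the cycle", but it points to Section 6.1, where the adjustment starts with the next cycle. The 24-hour report to the Study Chair (5.4), twice-weekly counts during severe cytopenia (5.6) and the weekly leadership call (14.5.2) provide oversight. None of them sets the dose of the next block.

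**The case against.** The strongest reply is that the permission is read partly out of silence. Section 6.1.1 describes treatment after a hematologic DLT only in terms of later cycles, and Section 6.1.3 and the CBC rule use eligibility counts as the mark of recovery. A site could conclude that dosing stops until the next cycle. That reading is available, and it is why the point cannot be put as an instruction to re-expose. But no section states the hold, and the restart sentence in 5.2.1 makes no exception for it.

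The second reply is structural. Hematologic toxicity has a check before every block and non-hematologic toxicity has none, so omitting within a cycle and reducing between cycles is a coherent scheme. Dose is otherwise set per cycle too. This may explain the different wording in 6.1.1 and 6.2.1. It does not settle what dose a patient with a declared DLT receives at the next block.

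Third, the consequence is small. In the three cases above the unreduced total never exceeds 75% of plan, and the adult escalation table shows no DLT in 2 evaluable patients at 40 mg, though 2 patients say little. Nothing forbids an earlier hold or reduction, and Section 10.1 lets the physician stop therapy. All of this stands and keeps the point minor.

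**Conclusion.** The gap is real and minor. Taken literally, Sections 5.2.1 and 6.1.1 allow the unreduced dose again in the cycle where a hematologic DLT was met, at lower counts than the reduced dose needs a cycle later. The excess is 33% to 67% in daily dose for the remaining one or two blocks. At 40 mg BID that is 120 mg (day-8 case) or 60 mg (the other two) over the cycle.

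Three stronger inferences are not supported:

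- **That the protocol orders re-exposure.** The permission comes from a restart rule with no DLT exception, and a hold is a possible reading.
- **That the MTD decision is distorted.** The DLT is already counted when the later block is given.
- **That every administration is 1.33 to 1.67 times too high.** Those are daily ratios. Per administration the range is 1.0 to 2.0.

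The totals assume that the DLT is found at a count before a block and that counts then recover enough for every remaining block. In cycles 2 and later, Sections 5.7 and 8.1 schedule counts only at cycle start and day 15 unless cytopenia or a dose adjustment triggers more, so a day-8 count there rests on 5.2.1 alone. The 75% ceiling belongs to these cases: a DLT met and resolved between two blocks would omit none. The documents give no frequency for any of this.

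**What to change.** In 6.1.1, apply the reduction to *subsequent doses, including any remaining 3-day block of the same cycle*.

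In 5.2.1, add that *restart in the same cycle at the unreduced dose applies only to count holds that do not meet a DLT criterion in 5.5.2*. If the intent is no further dosing until the next cycle, say that in 5.2.1 instead. The count thresholds in 5.2.1 and the deadline in 6.1.3 can stay.

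If the reduction starts mid-cycle, 6.1.2 also needs a sentence. It says that patients with a hematologic DLT "after one dose reductions must be removed from protocol therapy". A patient who omits block 2 for a DLT, restarts reduced on day 15 and then omits block 4 would fall below 75% and be removed partly for a block lost before the reduction. Add that only a new hematologic DLT arising after the first reduced dose counts, that blocks omitted before that dose do not count toward the 75% criterion for this purpose, and that delayed recovery from the first DLT is handled by 6.1.3.

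The cost is wording in three sections, with no new patients or tests, since weekly counts are already required after a hematologic DLT until recovery and after a hematologic dose adjustment. The downsides are a daily dose 25% to 40% lower for the rest of that cycle, possible mid-cycle dispensing of 10 mg tablets, and earlier use of the single permitted reduction.

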6.2 Dose Modifications for Non-Hematological Toxicity

- 6.2.1 Patients who have any dose-limiting non-hematological toxicity (as defined in [Section 5.5.1](#)) may continue on protocol therapy upon meeting eligibility lab requirements or Grade ≤ 1 but should receive subsequent doses with at least a 25% dose reduction (75% of the original dose). Please see dosing nomograms in [Appendix V](#). For patients ≥ 18 years of age with starting dose of 40 mg BID, dose should be reduced to 30 mg BID 3 days on, 4 days off per week (25% dose reduction).
- 6.2.2 If a non-hematological dose-limiting toxicity recurs after one dose reduction, the patient must be removed from protocol therapy.
- 6.2.3 Patients who have a dose-limiting non-hematological toxicity that does not resolve to Grade ≤ 1 or eligibility within 14 days after the planned start of the next treatment cycle (42 days from start of previous cycle) must be removed from protocol therapy

7.0 SUPPORTIVE CARE AND OTHER CONCOMITANT THERAPY

7.1 Concurrent Anticancer Therapy

Concurrent cancer therapy, including chemotherapy, radiation therapy, immunotherapy, or biologic therapy may NOT be administered to patients receiving study drug. If these treatments are administered the patient will be removed from protocol therapy.

7.2 Investigational Agents

No other investigational agents may be given while the patient is on study.

7.3 Supportive Care

Appropriate antibiotics, blood products, antiemetics, fluids, electrolytes and general supportive care are to be used as necessary. Please see COG Supportive Care guidelines at <https://childrensoncologygroup.org/index.php/cog-supportive-care-guidelines>. Based on the UV absorption properties of BAY 1895344 (elimusertib), patients should be instructed to use topical sun block and UV-blocking sunglasses during treatment with BAY 1895344 (elimusertib). Direct exposure of patients to sun light after administration should be avoided. Please see Patient Instructions for Sun Protection in [Appendix XIV](#).

BAY 1895344 (elimusertib) has low emetogenic potential. Please see COG Guidelines on Chemotherapy Induced Nausea and Vomiting for recommendations on prevention options https://childrensoncologygroup.org/downloads/COG_SC_CINV_Guidelines_Document.pdf.

7.4 Growth Factors

Growth factors are not approved for use on this study.

7.5 Concomitant Medications

In vitro, BAY 1895344 (elimusertib) is metabolized mainly by CYP3A4 and to a much lesser extent CYP1A1.

Strong inducers or inhibitors of CYP3A4 should be avoided from 14 days prior to enrollment to the end of the study. BAY 1895344 (elimusertib) is predicted to be a moderate inducer toward sensitive CYP3A4 substrates. Drugs that are considered sensitive or narrow therapeutic range CYP3A4 substrates should be avoided for the duration of protocol therapy. See [Appendix III](#) for a list of agents. Substrates of CYP2C8, 2C9, and 2C19 should be used with caution.

BAY 1895344 (elimusertib) was identified as an *in vitro* inhibitor of BCRP, P-gp, BSEP, OATP1B1, and OATP1B3. The risk for clinically relevant drug-drug interactions due to inhibition of BSEP is considered to be negligible, but substrates of BCRP, P-gp, OATP1B1, and OATP1B3 should be used with caution. BAY 1895344 (elimusertib) is not a P-gp or BCRP substrate.

Because of pH dependent solubility, antacid drugs, H2-blockers, and proton pump inhibitors may affect absorption and exposure of BAY 1895344 (elimusertib).

Because there is a potential for interaction of BAY 1895344 (elimusertib) with other concomitantly administered drugs, the case report form will capture the concurrent use of all other drugs, over-the-counter medications, or alternative therapies only in Cycle 1. [Appendix XV](#) – Patient Drug Interactions Handout and Wallet Card should be provided to patients and includes recommendations on medications to avoid due to potential interactions.

